Statistical Analysis Plan

Protocol Title:	A Multicenter, Open-label, Single-arm, Extension Study to Assess Long-term Safety of Evolocumab Therapy in Patients with Clinically Evident Cardiovascular Disease	
Short Protocol Title:	FOURIER-OLE	
Protocol Number:	20130295	
NCT Number:	NCT02867813	
Authors:	[REDACTED] [REDACTED] (PAREXEL), [REDACTED] (PAREXEL)	
Sponsor:	Amgen Inc. [name] [name] [contact]	
SAP Date:	Document Version	Date
	Original (v1.0)	10 June 2019
	Amendment 1 (v2.0)	21 December 2021
	Amendment 2 (v3.0)	08 March 2022

Version Number	Date (DDMMYYYY)	Summary of Changes, including rationale for changes
Original (v1.0)	10JUN2019	
Amendment 1 (v2.0)	21 DEC 2021	
Changes
 
1. Change one of the authors from [REDACTED] and then author added [REDACTED] [REDACTED] Rationale: Study lead statistician role had been transitioned to [REDACTED]. Study lead transition role transitioned from [REDACTED] to [REDACTED]. Study Statistician role also transition from [REDACTED]2. Update statistical analysis plan (SAP) version and date throughout this SAP Rationale: Statistical analysis plan was amended3. Removed long-term safety analysis set and related analysis from SAP and clarified the rationale in section 10. Rationale: The pre-specified planned analyses in the SAP focus on the long term safety data in the subjects who enrolled into this OLE study (i.e., OLE safety analysis set) rather than the long-term safety analysis set which also includes FOURIER subjects who did not rollover into this OLE study. We will include FOURIER data and OLE data from those that enrolled in the OLE for the analysis. More details will be provided in SAP section 9.4. Add the explanations for "ABI" and "PAD" in the list of abbreviations Rationale: To explain the abbreviation of a new definition added in section 5.25. Added explanation for "K-M" in the list of abbreviations as included for efficacy tables.6. Added new subgroup analysis in the list per request from Clinical team to analyze the long term exposure effect in subjects with evolocumab.7. Update the definition of planned covariates in section 4.1 Rationale: Since this study is for

	
estimation and summarizes descriptive statistics. Covariate analysis involves modelling; therefore, covariate analysis is not applicable for this study.
 
8. Update section 5 to include definition of censoring date and time to event Rationale: We need those to be able to compare the results of OLE vs FOURIER.
 
9. Provided more details on the definition of last dose date in section 5.1 and apparently updated language in definition for Enrollment date and Study day 1. Rationale: to clarify the definition in both in-clinic and non-clinic settings.
 
10. Change the definition of age in section 5.2 Rationale: To clarify age at enrollment is the subject's age in years as recorded on Demographics eCRF of the parent study
 
11. Remove the second paragraph in sections 6.1 and 6.2 Rationale: Sections 9.5 and 9.6 have covered the information
 
12. Update the definition of OLE CANTAB analysis set in section 6.3 Rationale: To clarify this analysis set and align with the protocol
 
13. Update section 8.3.2 to include imputation methods for handling CEC reviewed events and death date. Rationale: To be consistent with Fourier reporting.
 
14. Update the wording of the primary endpoint in Table 9-1 Rationale: This change is to clarify that all events listed are treatment emergent
 
15. Remove disease-related events from the primary summary of primary endpoint in Table 9-1 Rationale: These will be reclassified as AEs in the long-term safety analysis set
 
16. Updated section 9.3 to include COVID-19 related protocol deviations and important protocol deviations

--	--

	
Rationale: Per GDE-409220, the COVID-19 related PD and IPD will also be summarized and listed as per Amgen standard
 
17. Update the language in section 9.5.1 Analyses of Primary Endpoint Rationale: To clarify that all adverse event summaries will include not only Clinical Events Committee (CEC) reviewed events but also disease related events; to clarify that disease related events will be coded with Medical Dictionary for Regulatory Activities (MedDRA)
 
18. Remove the last two paragraphs in section 9.5.1 Rationale: The third paragraph has captured the information
 
19. Replace “serious AE” with “serious TEAE” in section 9.6.1 Rationale: To clarify only serious AEs which are treatment emergent will be summarized
 
20. Specify the analysis set in section 9.6.2 and 9.6.3 Rationale: To clarify that laboratory test results and vital signs will only be summarized based on the OLE safety analysis set
 
21. Update the wording in section 9.6.6 Exposure to Concomitant Medication Rationale: To clarify that concomitant medication analysis will use the terms as coded by WHO Drug
 
22. Add the description in section 9.6.6 Exposure to Concomitant Medication Rationale: To clarify that how to handle the completely blank start date.
 
23. Add one analysis in section 9.7 Rationale: Team agreed on adding a listing for events which occurred in the time between the subject's EOS date in FOURIER and the enrolment date of the OLE
 
24. Add the time point of End of Study (EOS), the assessments of Body weight, Concomitant therapy and Physical exam in Appendix A Rationale: To add the analysis windows at EOS visit, and add the

--	---

Amendment 2 (v3.0)	08 MAR 2021	
items of body weight, concomitant therapy and physical exam
 
25. Updated the analysis window for week 260 Rationale: to make sure the lipid assessments are properly included for the analysis
 
26. Update censoring date definition in section 5 for mortality endpoints Rationale: To incorporate the last known survival status information when censoring for mortality endpoints especially for those lost to follow up patients or patients that withdrew consent
 
27. Provided reasons for subjects from site which may be removed from analysis sets Rationale: The site which has issue to provide the source documentation for clinical trial data verification needs to be removed from analysis
 
28. Update the imputation methods for missing EOS date, survival status date and death dates. Rationale: to help address partial/missing EOS dates, survival status dates and death dates
 
29. Update the LDL-C subgroup to LDL-C<40 mg/dl in section 9.6.1 Rationale: LDL-C < 40 mg/dl is used to be consistent with other low LDL-C achievement analysis
 
30. Removed the toxicity shift table Rationale: Safety lab data were not collected in this study.
 
31. Updated the plot in appendix C based on the new censoring date Rationale: to reflect the new censoring date which considers the last known survival status date

--------------------	-------------	--

Table of Contents

Table of Contents	6
1. Introduction.....	10
2. Objectives, Endpoints and Hypotheses.....	10
2.1 Objectives and Endpoints.....	10
2.2 Hypotheses and/or Estimations.....	11
3. Study Overview	11
3.1 Study Design.....	11
3.2 Sample Size.....	12
4. Covariates and Subgroups	13
4.1 Planned Covariates	13
4.2 Subgroups.....	13
5. Definitions.....	14
5.1 Study Time Points	14
5.2 Demographic and Baseline-related Definitions.....	17
5.3 Other Study Related Definitions	19
6. Analysis Sets.....	22
6.1 OLE Safety Analysis Set	22
6.2 OLE CANTAB Analysis Set.....	22
7. Planned Analyses	22
7.1 Interim Analysis and Early Stopping Guidelines	22
7.2 Primary Analysis	22
8. Data Screening and Acceptance.....	22
8.1 General Principles	22
8.2 Data Handling and Electronic Transfer of Data	22
8.3 Handling of Missing and Incomplete Data	23
8.3.1 Patterns of Missing Data	23
8.3.2 Handling of Incomplete Dates.....	23
8.4 Detection of Bias	24
8.5 Outliers	25
8.6 Distributional Characteristics	25
8.7 Validation of Statistical Analyses	25
9. Statistical Methods of Analysis.....	25

UC	Ultracentrifugation
VLDL-C	Very low-density lipoprotein cholesterol

1. Introduction

The purpose of this Statistical Analysis Plan (SAP) is to provide details of the statistical analyses that have been outlined within the protocol amendment **3** for study 20130295, AMG 145 evolocumab dated **26 February 2020**. The scope of this plan includes interim analyses and the primary analysis that are planned and will be executed by the Amgen Global Biostatistical Science department unless otherwise specified.

2. Objectives, Endpoints and Hypotheses

2.1 Objectives and Endpoints

Objectives	Endpoints
Primary	

To describe the safety and tolerability of long-term administration of evolocumab	
Subject incidence of adverse events

Secondary	

To describe the effects of long-term administration of evolocumab on low density lipoprotein cholesterol (LDL-C) levels	
Percent change of LDL-C from baseline at each scheduled visit

To describe the effects of long-term administration of evolocumab in subjects achieving an LDL-C level of < 40 mg/dL (1.03 mmol/L)	
Achievement of an LDL-C level < 40 mg/dL (1.03 mmol/L) at each scheduled visit

Exploratory	
In subjects who completed the EBBINGHAUS study (Study 20130385): 
To evaluate long-term change over time in executive function, as assessed by the Cambridge Neuropsychological Test Automated Battery (CANTAB) Spatial Working Memory (SWM) strategy index of executive functionTo evaluate long-term change over time in working memory, as assessed by the CANTAB SWM test between-errors scoreTo evaluate long-term change over time in memory function, as	In subjects who completed the EBBINGHAUS study: Change from baseline in 
SWM strategy index of executive functionSWM between-errors scorePAL total errors adjustedRTI median 5-choice reaction time

assessed by the CANTAB Paired Associates Learning (PAL) test
 
• To evaluate long-term change over time in psychomotor speed, as assessed by the CANTAB Reaction Time (RTI) test	

In all subjects:
 
• To describe the effects of long-term administration on non-high-density lipoprotein cholesterol (non-HDL-C), apolipoprotein B (ApoB), total cholesterol, lipoprotein(a) (Lp[a]), triglycerides, high-density lipoprotein cholesterol (HDL-C), LDL-C, very low-density lipoprotein (VLDL-C), and apolipoprotein A1 (ApoA1) levels• To describe the effects of long-term administration of evolocumab on subject incidence of death and cardiovascular events of interest	
In all subjects:
 
▪ Change and percent change from baseline at each scheduled visit in each of the following lipid parameters:
○ Total cholesterol○ Triglycerides○ LDL-C○ HDL-C○ VLDL-C○ non-HDL-C○ ApoA1○ ApoB○ Lp(a)▪ Subject incidence of events positively reviewed by the CEC:
○ All deaths○ Cardiovascular events of interest:
▪ Myocardial Infarction (MI)▪ Stroke▪ Coronary revascularization▪ Hospitalization for unstable angina▪ Hospitalization for heart failure▪ Transient Ischemic Attack (TIA)

2.2 Hypotheses and/or Estimations

The primary clinical hypothesis is that long-term exposure of evolocumab will be safe and well tolerated in subjects with clinically evident atherosclerotic cardiovascular disease (CVD).

3. Study Overview

3.1 Study Design

This is a multicenter, open-label extension study designed to assess the long-term safety of evolocumab in subjects who completed the FOURIER study (Study 20110118), a randomized placebo-controlled study of evolocumab in subjects with clinically evident

atherosclerotic CVD on stable effective statin therapy. Eligible subjects at sites participating in FOURIER OLE who have signed the FOURIER OLE informed consent may be enrolled at the completion of FOURIER. Enrollment of eligible subjects may be limited at the site level to maintain a 1:1 ratio between the following subject populations:

- subjects with \geq 2 years of study exposure in FOURIER and
- subjects who have less than 2 years of study exposure in FOURIER and did not participate in EBBINGHAUS

In this study (FOURIER OLE), laboratory assessments will be performed at week 12 and thereafter approximately every 24 weeks from day 1; the corresponding blood samples will be processed using a central laboratory. To preserve the integrity of FOURIER blinding, no local lipid assessments may be performed until either FOURIER is unblinded or at least 12 weeks after a subject's last administration of FOURIER investigational product (evolocumab or placebo), whichever is first.

Upon enrollment in this study (FOURIER OLE), subjects will receive evolocumab 140 mg every 2 weeks (Q2W) or 420 mg monthly (QM), according to their preference. Frequency and corresponding dose of administration can be changed at any scheduled time point where evolocumab is supplied to the subject, provided the appropriate supply is available. It is recommended that subjects continue the same background LLT, including statin, as taken during FOURIER.

This study will continue for 260 weeks (approximately 5 years). Subjects ending administration of evolocumab should continue study assessments until the end of study (EOS).

All subjects will be followed and complete procedures/assessments from enrollment through the date of study termination unless the subject has withdrawn consent, irrespective of whether the subject is continuing to receive treatment. All deaths and cardiovascular events of interest (MI, stroke, coronary revascularization, hospitalization for unstable angina, hospitalization for heart failure, and transient ischemic attack [TIA]) will be reviewed by an independent external Clinical Events Committee (CEC), using standardized definitions.

3.2 Sample Size

It is estimated approximately 5000 subjects who completed the FOURIER study will be enrolled. Based on a sample size of 5000 subjects, [Table 3-1](#) lists the width of 95% confidence intervals for a range of various underlying adverse event rates.

Table 3-1. Confidence Interval Width for Adverse Event Rates

Percent Underlying Adverse Event	Width of 95% Confidence Interval
0.01%	0.056%
0.05%	0.124%
0.10%	0.176%
1.00%	0.552%
2.00%	0.776%
3.00%	0.946%
4.00%	1.086%
5.00%	1.208%

4. Covariates and Subgroups

4.1 Planned Covariates

Not applicable.

4.2 Subgroups

The planned subgroups include the following:

- Baseline age (< 65 years, ≥ 65 years; < 75 years, ≥ 75 years)
- Sex (male, female)
- Race (white, non-white)
- Prior non-hemorrhagic stroke (yes, no)
- Symptomatic PAD (yes, no)
- Prior MI (No, < 1 year, 1 - < 2 years, ≥ 2 years)
- Baseline PCSK9 level (< median, ≥ median)
- Baseline LDL-C by quartiles (Q1, median, Q3)
- Baseline HDL-C by quartiles (Q1, median, Q3)
- Baseline triglycerides by quartiles (Q1, median, Q3)
- Baseline hsCRP (< 2 mg/L, ≥ 2 mg/L)
- Ezetimibe use at baseline (yes, no)
- ACC/AHA high statin background therapy intensity at baseline (yes, no)
- History of type 2 diabetes (yes, no)
- Heterozygous Familial Hypercholesterolemia (HeFH) at OLE enrollment (definite, probable, neither definite nor probable)
- **Subjects who were randomized to and received evolocumab group in the parent (i.e., FOURIER) study with ≥ 7 years of the combined exposure for evolocumab across the parent study and this OLE study**

5. Definitions

5.1 Study Time Points

Baseline

The baseline value is defined as the subject's baseline value from the parent study, unless otherwise specified.

First Dose Date of Investigational Product (IP)

For each subject, the first dose date of IP is the date of the first administration of evolocumab in this OLE study.

End of Investigational Product (EOIP) Date

For each subject, end of investigational product is the date reported on End of Investigational Product Administration eCRF.

Last Dose Date of Investigational Product

For each subject, the last dose date of investigational product is defined as the date of the last administration of investigational product (evolocumab or placebo).

If the last dose was administered in-clinic, then the Last IP Dose Date is the last start date captured on the IP Administration (In-Clinic) eCRF page.

If the last dose was administered at a non-investigator site location, then the Last IP Dose Date is defined as the final dose date reported by the subject on the Non-Clinic Final Investigational Product Dose Date eCRF page.

End of Study (EOS) Date

For individual subject, the end of study date is defined as the last day that protocol-specified procedures are conducted for an individual subject, including safety follow-up and survival assessment. The EOS date is recorded on the End of Study eCRF.

Enrollment Date

The enrollment date for each subject is recorded on the Subject Enrollment eCRF **in the OLE study.**

Study Day 1

The date of the first administration of evolocumab in the OLE study or the **enrollment date** for subjects who are not administered any dose of evolocumab.

Study Day

For each subject, and for a given date of interest, study day is defined as the number of days since study day 1:

Study day = (date of interest – study day 1 date) + 1

If the date of interest is prior to the study day 1:

Study day = (date of interest – study day 1 date)

Study End Date

The study end date is the last EOS date of all enrolled subjects.

Endpoint Categories

All time-to-**first**-event endpoints in this study are categorized below.

- Composite
 - time to cardiovascular death, myocardial infarction, hospitalization for unstable angina, stroke, or coronary revascularization, whichever occurs first
 - time to cardiovascular death, myocardial infarction, or stroke, whichever occurs first
 - time to cardiovascular death or hospitalization for worsening heart failure, whichever occurs first
 - time to ischemic fatal or non-fatal stroke or transient ischemic attack, whichever occurs first
 - time to the first fatal and non-fatal myocardial infarction
 - time to the first fatal and non-fatal stroke
- Non-mortality
 - time to the first coronary revascularization
- Mortality
 - time to cardiovascular death
 - time to coronary death
 - time to death by any cause

Censoring date

Endpoints are censored differently according to the endpoint **categories**. The censoring schema are described in below:

- censoring date for the composite and non-mortality endpoints is the EOS date in the OLE study.
- censoring (or time-to-event) for mortality endpoints are detained in appendix C.

Time-to-first-event Definition

For the time-to-first-event analysis based on combined the parent and OLE data, the events adjudicated as positive in the parent study and occurred prior to or on subject last confirmed survival status date in the parent study (i.e., primary analysis in the parent study; please see the definition in the parent study SAP version 3.1 dated Aug 09, 2016) are included in addition to the events reviewed as positive in the OLE study (defined as below).

For the time-to-first-event analysis based on the OLE data only, mortality events reviewed as positive and occurred prior to or on later of (the EOS date or last known survival status date from eCRF page(s) in this OLE study) and non-mortality events reviewed as positive and occurred prior to or on the EOS date are included.

- For those subjects who already experience such event in the parent study, their time to event and censor flag are same as those in the parent study.
- For those subjects who didn't experience such event in the parent study, the derivation of the time-to-event and censoring date is presented below

For analyses combined both the parent study and this OLE study		
Endpoint	Time-to-first-event for subjects with events	Censoring date for subjects without events
Composite or Non-mortality	First event onset date reviewed by CEC in OLE study – randomization date in the parent study +1	EOS date in OLE study
Mortality	Death endpoint date reviewed by CEC in OLE	For subjects who died not due to death endpoint, the censoring date is the death

	study – randomization date in the parent study +1	date (reviewed by CEC) in OLE study For remaining subjects, the censoring date is max (EOS date, last known survival status date from eCRF page(s)) in the OLE study
For analyses based on OLE data only		
Composite or Non-mortality	First event onset date reviewed by CEC in OLE study – enrolment date in OLE study +1	EOS date in OLE study
Mortality	Death endpoint date reviewed by CEC in OLE study – enrolment date in OLE study +1	For subjects who died not due to death endpoint, the censoring date is the death date (reviewed by CEC) in OLE study For remaining subjects, the censoring date is max (EOS date, last known survival status date from eCRF page(s)) in the OLE study

Patient-years of follow-up for treatment emergent adverse events

For analyses based on combined both the parent study and this OLE study:

- 1) Subjects had events: date (first event) – date (first dose date in FOURIER) + 1
- 2) Subjects didn't have events: min [date (EOS in OLE), date (last dose date in OLE)+30] – date (first dose date in FOURIER) + 1

For analyses based on OLE study:

- 1) Subjects had events: date (first event in OLE) – date (first dose date in OLE) + 1
- 2) Subjects didn't have events: min [date (EOS in OLE), date (last dose date in OLE)+30] – date (first dose date in OLE) + 1

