Vital status must be obtained for all subjects within the limits of local law. This includes subjects who may have discontinued study visits with or without withdrawing consent and should include interrogation of public databases, if necessary. If deceased, the date of death should be obtained and reported.

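### SAP 5.1 does not confine the longer cut-off for deaths to the mortality endpoints, so on a literal reading deaths after EOS enter composites whose event-free subjects are censored at EOS

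*SAP*

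**What the plan says.** SAP 5.1 (Study Time Points) sorts all time-to-first-event endpoints into three categories: composite, non-mortality and mortality. There are six composites.

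- Three name CV death: "time to cardiovascular death, myocardial infarction, or stroke, whichever occurs first", "time to cardiovascular death or hospitalization for worsening heart failure, whichever occurs first", and a five-part composite that adds unstable angina and coronary revascularization to the first of these.
- Three have a fatal MI or fatal stroke part: "time to ischemic fatal or non-fatal stroke or transient ischemic attack, whichever occurs first", "time to the first fatal and non-fatal myocardial infarction", and the matching stroke endpoint.

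The inclusion sentence for the OLE-only analysis has only two windows. Deaths are included as "mortality events reviewed as positive and occurred prior to or on later of (the EOS date or last known survival status date"; for the rest, "non-mortality events reviewed as positive and occurred prior to or on the EOS date are included". The combined parent and OLE analysis takes its OLE events under the same rule.

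On censoring, the section states: "censoring date for the composite and non-mortality endpoints is the EOS date in the OLE study". The derivation table dates a composite event at the first onset reviewed by the CEC and sets no limit at EOS. Only the mortality row censors survivors at the later of EOS and the last known survival date.

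The plan foresees survival information after EOS. Protocol 7.2.2 requires vital status for all subjects: "This includes subjects who may have discontinued study visits with or without withdrawing consent". SAP 8.3.2 imputes a missing death date as the latest of several dates including EOS, so an imputed death never falls before EOS and may fall after it.

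**The concern.** Take two subjects who leave the study at year 2 without an event. Public records show that one died of a CV cause at year 4 and that the other was alive at year 4. On a literal reading, the first is a composite event at year 4 and the second is censored at year 2. Time after EOS then enters the composite only for subjects who die in it, and non-fatal events in that time are never counted. The pure mortality endpoints avoid this, because their survivors are followed to the same date as their deaths.

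SAP 9.5.3 plans crude incidence, exposure-adjusted rates and yearly K-M estimates of positively reviewed events, for the OLE alone and for both studies combined. If the composites are reported this way, the K-M estimates would mix two ascertainment windows. Two programmers could also derive different composites from the same text.

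**Working it through.** **Step 1. The text.** Sorted by event type, a CV death is a mortality event on any ordinary reading, so it takes the longer window even inside a composite. Sorted by endpoint category, the longer window belongs to the Mortality category, but then the inclusion sentence gives composites no window of their own. For fatal MI and fatal stroke, dated by onset, the SAP does not say whether they are mortality events.

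**Step 2. Inputs.** From the documents: about 5000 subjects and 260 weeks (about 5 years). There is no stated composite rate, early-exit rate or tracing rate to reproduce, so these are assumptions:

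- composite hazard 3.0 per 100 person-years, of which CV death is 0.5 or 1.0;
- early EOS at 1%, 3% or 6% per year, unrelated to risk;
- vital status traced to year 5 in 25%, 50% or 100% of early leavers.

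This gives 2 × 3 × 3 = 18 scenarios, each simulated with 400,000 subjects. The true 5-year risk is 1 − exp(−0.03 × 5) = 13.9%.

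**Step 3. Rules compared.**

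- A, literal: non-fatal events to EOS, CV deaths to the last survival date, event-free subjects censored at EOS.
- B: every component to EOS only.
- C: events as in A, but event-free subjects censored at the last survival date.

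| CV death per 100 PY | Early EOS per year | Traced | A: rate | B: rate | A: 5-year K-M | B: 5-year K-M | C: 5-year K-M | A: crude | Extra deaths per 5000 |
|---|---|---|---|---|---|---|---|---|---|
| 0.5 | 1% | 25% | 3.004 | 3.000 | 13.95% | 13.94% | 13.87% | 13.62% | 1 |
| 1.0 | 3% | 50% | 3.044 | 3.007 | 14.13% | 13.96% | 13.62% | 13.15% | 9 |
| 1.0 | 6% | 100% | 3.165 | 3.014 | 14.69% | 13.99% | 12.78% | 12.78% | 32 |

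The rows are the smallest, a middle and the largest case. The K-M gaps are 13.95 − 13.94 = 0.01, 14.13 − 13.96 = 0.17 and 14.69 − 13.99 = 0.70 points. The rate gaps run from 0.004/3.000 = 0.1% to 0.151/3.014 = 5%.

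In all 18 scenarios A exceeded B on rate and K-M, and B matched the truth within simulation error. Crude incidence under A was 12.2% to 13.8%, below the true risk every time. C was too low when many leavers were traced, because it adds survivor time in which non-fatal events are not counted.

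**Step 4. Exit related to risk.** Suppose the CV death hazard doubles after exit, exit times are uniform over 5 years and all leavers are traced. With CV death hazard c, non-fatal hazard n and exit fraction p, B estimates 1 − exp(−5(c + n)). The true risk is (1 − p)[1 − exp(−5(c + n))] + p[1 − exp(−5(2c + n)) × (exp(5c) − 1)/(5c)].

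- p = 10%, c = 1%, n = 1% per year: B is 1 − exp(−0.10) = 9.52%. The truth is 0.9 × 9.516% + 0.1 × [1 − 0.8607 × 1.0254] = 9.74%. A, by simulation, is 9.99%, about 0.25 points high; B is about 0.22 low.
- p = 20%, c = 2%, n = 1% per year: B is 1 − exp(−0.15) = 13.93%. The truth is 0.8 × 13.929% + 0.2 × [1 − 0.7788 × 1.0517] = 14.76%. A, by simulation, is 15.77%, about 1.0 point high; B is about 0.8 low.

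In these cases the gap between A and B (about 0.5 and 1.8 points) is not the bias of A. Part of it is the shortfall of B under informative exit.

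**The case against.** The strongest reply is that the longer window was never meant for composites. SAP 5.1 ties censoring to endpoint category, and its derivation table puts composite and non-mortality endpoints in one row with EOS censoring. The change log gives mortality endpoints as the only reason for introducing the survival date. On that reading there is no bias. This stands as a tenable reading, but the inclusion sentence does not say it. The Appendix C figure is not available to settle the matter, and the text cites it for mortality endpoints only.

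Other limits also stand:

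- Patient-years are defined only for treatment-emergent adverse events, so the effect on rates assumes that person-time runs to event or censoring.
- The composites appear in SAP 5.1 but not in Table 9-1, and SAP 9.5.3 does not name them; their K-M reporting is inferred.
- EOS already includes survival assessment, record searches are partly optional, and a death must be classified by the CEC to a qualifying cause. All of this limits the number of deaths concerned.
- The study is descriptive, with no planned inference.

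A reader might infer that all six composites are certainly biased upward, or that the comparison of former FOURIER arms is distorted. The documents support neither. Only three composites name CV death, the category reading gives zero bias, and nothing in the documents shows that exit or tracing differs by arm.

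**Conclusion.** The point holds as an unresolved rule which, followed literally, gives composite K-M estimates that are too high. It is firm for the three composites that name CV death and open for the three with fatal MI or fatal stroke.

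The size is unknown and probably small. With exit unrelated to risk, the rise across the assumed scenarios is 0.01 to 0.7 points on a 5-year risk of about 13.9%, with 0.17 points (about 9 deaths per 5000) in a middle case. Those limits belong to the chosen inputs; heavier exit or a higher CV death rate would widen them. The harsh case with 20% exit gives about 1 point, and there the EOS-only estimate is itself low because exit is informative. It would be wrong to conclude that every planned summary is inflated: crude incidence stayed below the true risk in all 18 scenarios.

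**What to change.** Add to SAP 5.1: *For composite endpoints (OLE-only and combined), all components, including fatal ones, count only if they occurred on or before the OLE EOS date; deaths after EOS contribute to the mortality endpoints only.* Leave the mortality-endpoint censoring as it is.

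This matches the composite censoring already written and closes the gap for fatal MI and fatal stroke. Extending composite censoring to the survival date is not a good alternative, for the reason shown under rule C.

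The cost is one sentence and one date condition in the derivation. A few traced deaths leave the composites but remain in the mortality endpoints. If exit is related to risk, the composite estimate will be somewhat low, which the report should state.
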